The efficacy of SWORD Phoenix has already been demonstrated in two previous feasibility studies conducted at Hospital da Prelada, Porto, Portugal, between December 2016 and March 2018 (Clinical trial IDs: NCT03047252 and NCT03045549). These were two parallel-group studies, comparing the clinical evolution of patients submitted to an 8-week rehabilitation program after THA or TKA, divided into two distinct groups: the experimental group, which performed a home-based rehabilitation program using SWORD Phoenix, and the control group, which was also engaged in a home-based rehabilitation program, but with conventional physiotherapy instead. Geographical location was used as the allocation criterion, with patients living within the city's administrative limits allocated to the conventional physiotherapy group and patients living outside the city's administrative limits allocated to the experimental group. Results from the experimental group were superior to those from the conventional physiotherapy group in all outcome measures, and adverse effects rates were similar in both groups. The main results of the TKA study were already published ²⁸, and the main results of the THA study are in publication route.

More recently, a new version of the system was developed, where the possibility to execute bilateral exercises was added, focusing not only on the rehabilitation of the affected limb, but also on muscular reinforcement of the contralateral limb. As such,

a new clinical study was designed, aiming at exploring the clinical impact of this update on the therapeutic program (bilateral).

The present study is a single-center, prospective, single-arm, historical control study, designed to evaluate the clinical outcomes of a bilateral home-based rehabilitation program using **SWORD Phoenix®**. The clinical outcomes will be compared to those of the above-mentioned feasibility studies. The investigation hypothesis is that the clinical outcomes of the bilateral exercise program will be superior to those of the unilateral exercise program.

2. Study Outcomes

The aim of the studies is to evaluate the clinical impact of a home-based bilateral rehabilitation program after THA or TKA, using **SWORD Phoenix®**.

a) Primary outcome

The primary outcome will be the change in patient performance compared to the baseline, measured through the TUG.

b) Secondary outcomes

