- The change in patient reported outcomes, measured by HOOS and KOOS scales, as compared to baseline evaluation
- The change in the maximum amplitude of joints movements, as compared to baseline evaluation

3. Sample size estimate

Sample size estimation calculations were performed taking into consideration the primary outcome measure - Timed up and Go (TUG) test score. Calculations were based on the baseline TUG distribution of the participants in the two previous feasibility studies (total n=131; mean 18,00 seconds; sd=6,3) and on a Minimal Clinical Significant Change of 2.27 seconds as reported by Yuksel *et al.*²⁹.

Considering a power of 80%, a two-sided 0.05 significance level and an allocation rate of 2:1, 216 patients (144 in this study; 72 historical control) would be necessary to detect a 2.27 seconds difference against the historical control.

4. Inclusion criteria

- a) Patients over 18 years old
- b) Clinical and imaging evidence of hip/knee osteoarthritis
- c) Indication for total hip or knee replacement according to the patient's orthopedic surgeon
- d) Ability to walk unaided, with unilateral or bilateral support
- e) Availability of a caregiver to assist the patient after surgery

5. Exclusion criteria

- a) Patients admitted for revision of total hip/knee replacement
- b) Contralateral hip or knee osteoarthritis severely limiting patient mobility and ability to comply with a rehabilitation program
- c) Aphasia, dementia or psychiatric comorbidity interfering with the communication or compliance to the rehabilitation process
- d) Respiratory, cardiac, metabolic or other condition incompatible with at least 30 minutes of light to moderate physical activity
- e) Major medical complications occurring after surgery that prevent the discharge of the patient within 10 days after the surgery
- f) Other medical and/or surgical complications that prevent the patient from complying with a rehabilitation program
- g) Blind and/or illiterate patients
- h) Patients residing outside a 30km radius from the investigation center

6. Methods for identifying and recruiting patients

All patients admitted for total hip or knee replacement during the study period will

be screened for inclusion and exclusion criteria.

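### The sample size of 216 (144 + 72) is what a one-sided 0.05 test needs; at the stated two-sided 0.05 level the same inputs give about 70% power, not 80%.

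*Combined protocol and SAP*

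**What the plan says.** Section 3 (Sample size estimate) gives all the inputs together:

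- Variability: the baseline TUG distribution of the two earlier feasibility studies, "total n=131; mean 18,00 seconds; sd=6,3".
- Target: "to detect a 2.27 seconds difference against the historical control".
- Power: "Considering a power of 80"%.
- Level, allocation (new patients to historical controls) and result: "a two-sided 0.05 significance level and an allocation rate of 2:1, 216 patients (144 in this study; 72 historical control").

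The section mentions no dropout allowance, baseline-to-follow-up correlation or covariate adjustment. Section 15 (Results analysis) names no statistical test and no other significance level. The introduction states a directional hypothesis, that "the clinical outcomes of the bilateral exercise program will be superior to those of the unilateral exercise program", but no one-sided test is specified anywhere.

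**The concern.** The stated sidedness and the stated sample size contradict each other. A reader who enters the section 3 inputs into the usual formula does not get 216, and the gap is far too large to be rounding.

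The 80% figure is what an ethics committee or reader will rely on when interpreting a non-significant result. If power is nearer 70%, such a result is weaker evidence against a 2.27 s benefit than the protocol implies. The contradiction also leaves sidedness open. Since section 15 names no test, a one-sided 5% analysis could later be defended by pointing to the sample size, and a two-sided one by pointing to the text. In a non-randomised comparison with historical controls, that choice should be settled before the data are seen.

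**Working it through.** **Inputs (all from section 3).** SD = 6.3 s; difference = 2.27 s; power 80% (z = 0.842); two-sided 0.05 (z = 1.960; the one-sided value would be 1.645); two new patients per control.

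**Formula.** Comparison of two means, normal approximation:

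n(control) = (1 + 1/2) × (z_α + z_β)² × SD² / difference²

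Here SD²/difference² = 39.69/5.1529 = 7.702.

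**Reproducing 216.**

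| Calculation | n(control) before rounding | Controls + new patients | Total |
|---|---|---|---|
| Two-sided 0.05, 80% power (as stated) | 1.5 × (1.960 + 0.842)² × 7.702 = 90.7 | 91 + 182 | 273 |
| One-sided 0.05, 80% power | 1.5 × (1.645 + 0.842)² × 7.702 = 71.4 | 72 + 144 | 216 |

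With the noncentral t distribution the two-sided requirement is 92 + 184 = 276, and the one-sided requirement is again 72 + 144 = 216.

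**Other explanations tried at two-sided 0.05 and 80% power.**

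- 1:1 allocation: 121 + 121 = 242.
- Rank-test efficiency adjustment: 286 (273/0.955) or more.
- SD and difference varied within rounding (6.25 to 6.35 s; 2.265 to 2.275 s): 267 to 279.

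None gives 216. A dropout allowance cannot explain it either, because it would raise the total above 273.

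Lowering the power instead of changing the sidedness also gives 216: two-sided 0.05 with 70% power yields 1.5 × (1.960 + 0.524)² × 7.702 = 71.3, so 72 + 144. This is the same shortfall seen from the other side.

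**Power of the planned numbers.**

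- Standard error = 6.3 × √(1/144 + 1/72) = 0.909 s.
- Standardised difference = 2.27/0.909 = 2.496.
- Two-sided 0.05: Φ(2.496 − 1.960) = 70.4% (noncentral t: 70.0%). Rounding of SD and difference moves this only between 69.5% and 71.3%.
- One-sided 0.05: Φ(2.496 − 1.645) = 80.3% (noncentral t: 80.1%).
- Difference detectable with 80% power, two-sided: (1.960 + 0.842) × 0.909 = 2.55 s.

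**Shortfall.** 273 − 216 = 57 patients, and 57/273 = 21%. By group this is 182 − 144 = 38 new patients and 91 − 72 = 19 controls.

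**The case against.** Nobody disputes the arithmetic. The strongest reply is that 70% is not the power of the trial. The 6.3 s is the spread of TUG at baseline, whereas the primary outcome is change from baseline to 8 weeks, and the documents give neither an SD of change nor a correlation. If baseline and follow-up SDs are both taken as 6.3 s (an assumption), two-sided power at 144/72 depends on the correlation:

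| Correlation | Change score | ANCOVA |
|---|---|---|
| 0.3 | 56% | 74% |
| 0.5 | 70% | 82% |
| 0.6 | 80% | 88% |
| 0.7 | 90% | 94% |

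This stands as a condition on the 70%. It does not rescue section 3, which uses 6.3 s without adjustment and claims no gain from correlation. Two-sided 80% power at 144/72 needs an effective SD of about 5.61 s, a figure the protocol never gives. It corresponds to a correlation of about 0.60 for change scores or 0.45 for ANCOVA. The true power could also lie below 70%.

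Three further points have some force:

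- The use of a one-sided critical value is inferred from the exact match; the protocol does not show its formula.
- Because the hypothesis is directional, the slip may be in the words rather than in the number. Either way, text and number disagree.
- The power figure assumes 72 usable controls. The 131 feasibility participants span both arms of both studies, and arm sizes are not given. With SD 6.3 s and 144 new patients, 60 controls would give about 65% power and 91 about 77%.

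**Conclusion.** The concern holds. On the protocol's own inputs, 216 patients do not provide 80% power at two-sided 0.05. They provide about 70%, with 80% reached at 2.55 s instead of 2.27 s. Meeting the claim as written would take 273 patients (276 by the t-test).

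These figures assume an SD of 6.3 s applied directly to the outcome, 72 historical controls and no attrition. Any loss of patients would lower power further. That the contradiction exists depends on none of the unknowns, because every quantity needed to show it is stated in section 3. It should be corrected, since it concerns the headline design claim for the primary outcome.

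**What to change.** Keep the two-sided 0.05 test and the planned enrolment, and replace the closing sentence of section 3 with wording such as:

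> *With 144 new patients and 72 historical controls, an SD of 6.3 s (baseline TUG in the feasibility studies) and a two-sided 0.05 level, power is about 70% to detect a difference of 2.27 s and 80% to detect 2.55 s.*

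Naming 6.3 s as a baseline SD stops the figure being read as the power for change scores. Section 15 should state that the primary comparison is tested at two-sided 0.05. The cost is wording only: no extra patients, and a stated power of 70% in place of 80%.

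Two other routes would also remove the contradiction, at a higher price:

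- **Enlarge the study.** Keeping 80% at two-sided 0.05 with 2:1 allocation takes 182 + 91 = 273 (276 by the t-test), if 91 suitable controls exist. If controls stay at 72, the new arm would need 1/[(2.27/(6.3 × 2.8016))² − 1/72] ≈ 377, or 378 after rounding up, where 2.8016 is z_α + z_β at two-sided 0.05 and 80% power.
- **Declare a one-sided 0.05 test.** This makes 216 correct, but it must be specified and justified before analysis, and it doubles the false-positive rate in the favourable direction from 2.5% to 5%.

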When a potential candidate is identified, the local investigator will approach the candidate and explain the study in detail. The prospective candidate will be given the patient information document and sufficient time to consider whether he wishes to participate in the study.

Subsequently, the prospective candidate will be given opportunity to clarify any doubts, after which the informed consent form will be signed and dated in duplicate by the patient and the investigator. Only then will the randomization and baseline assessments be performed.

7. Informed consent

Informed consent will be delivered in paper format (see annex), informing individuals of their free will to drop out of the study, without any prejudice to their health assistance or medical attention. It includes information on collected data confidentiality and its publication potential in scientific journals, respecting all due ethical standards.

Finally, it assures the individual that he was correctly informed about the study, requiring the signature from both the patient and one of the study researchers.

8. Data anonymization

Numerical codes will be attributed to each study participant. As soon as possible, all the information from the questionnaires will be transferred to digital data bases and the documents kept in a specific location at SWORD Health, SA headquarters, with restricted access.

9. Scales and assessment tools

Several studies suggest that the outcomes should be measured not only in terms of range of motion, which is considered a poor marker of implant success and patient satisfaction^{9,30-32} but also using patient-reported outcomes and a performance test^{33,34}. As such, results will be evaluated according to three outcome measures: **a)** a performance test; **b)** patient-reported outcomes (using HOOS and KOOS scales); **c)**

range of motion of the hip or knee.

a) Performance test

Timed up and Go (TUG) test was selected as a performance test, which measures the time the patient takes to rise up from a chair, walk three meters, turn around, walk again towards the chair and sit. This test was chosen as it is simple and practical, quick and easy to administer, has high inter-rater reliability ³⁵ and has been demonstrated to predict both short- ³⁶ and long-term ^{37,38} function, following arthroplasty.

Instructions to perform the test:

- 1) Select a chair with armrests and a seating height of 44-47 cm

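### The 144 new patients and 72 historical controls give about 70% power at the stated two-sided 0.05 level, not 80%, and section 3 shows neither the evaluable control count nor any allowance for loss to week 8

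*Combined protocol and SAP*

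**What the plan says.** Section 3 (Sample size estimate) takes its SD from "the baseline TUG distribution of the participants in the two previous feasibility studies (total n=131" and gives the summary as "total n=131; mean 18,00 seconds; sd=6,3". It sets 80% power and "a two-sided 0.05 significance level", and concludes that "an allocation rate of 2:1, 216 patients (144 in this study; 72 historical control) would be necessary". The target is a gap of 2.27 s in TUG between the new cohort and the earlier patients.

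The introduction describes a single-arm study with historical controls. These come from two feasibility studies run between December 2016 and March 2018, whose patients were "divided into two distinct groups: the experimental group, which performed a home-based rehabilitation program using SWORD Phoenix", and a control group given conventional home physiotherapy. The hypothesis is that the bilateral programme is superior to the unilateral one. Another sentence there says only that outcomes will be compared with those of the feasibility studies.

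Section 15 (Results analysis) evaluates outcomes from baseline to 8 weeks and removes participants with adherence below 43% from the per-protocol analysis. Section 7 (Informed consent) tells patients that they may withdraw. Section 3 mentions no loss in either cohort.

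Section 6 says of the steps after consent: "Only then will the randomization and baseline assessments be performed".

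**The concern.** Two things in section 3 do not fit the design.

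First, the total does not follow from the stated inputs. A reader who repeats the calculation at the stated two-sided level gets a larger number.

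Second, the control number is produced as an output of a 2:1 ratio. In a study whose controls were all treated before it began, the number of usable controls is a fact about an existing database. It should go in as an input, with power or detectable difference coming out. The only count given is 131, over both treatment groups of both earlier studies. How many had the unilateral Phoenix programme, and how many of those have TUG at both baseline and week 8, is not stated.

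The interpretation of a null result is at stake. If the study was sized for 80% but has nearer 65 to 70%, a failure to show superiority says less than the plan implies, and a reader cannot tell how much less.

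**Working it through.** **Inputs, all from section 3:** difference d = 2.27 s; SD s = 6.3 s; alpha 0.05, stated as two-sided; power 80%; 2:1; 144 new, 72 control, 216 in total.

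**Reproducing 216.** With n controls and 2n new patients, n = 1.5 × (s × k / d)², where k is the sum of the normal quantiles for alpha and power.

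- Two-sided 0.05: k = 1.9600 + 0.8416 = 2.8016. (6.3 × 2.8016 / 2.27)² = 60.46, and × 1.5 = 90.7. This gives 91 controls + 182 new = 273.
- One-sided 0.05: k = 1.6449 + 0.8416 = 2.4865. (6.3 × 2.4865 / 2.27)² = 47.62, and × 1.5 = 71.4. This gives 72 + 144 = 216, the plan's figure exactly.

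**Power of 144 against 72.** The standard error is 6.3 × √(1/144 + 1/72) = 6.3 × 0.14434 = 0.9093, and 2.27 / 0.9093 = 2.496.

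- Two-sided: Φ(2.496 − 1.960) = 70.4%.
- One-sided: Φ(2.496 − 1.645) = 80.3%.
- Using the t distribution instead gives 70.0% and 80.1%.
- Detectable difference at 80% power, two-sided: 2.8016 × 0.9093 = 2.55 s.

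**Other evaluable numbers.** The documents give neither the Phoenix group sizes nor a loss rate, so these are assumed examples. The formula is the same.

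| Assumption | New | Controls | Two-sided | One-sided |
|---|---|---|---|---|
| As stated | 144 | 72 (55% of 131) | 70.4% | 80.3% |
| About half of 131 | 144 | 65 | 67.4% | 77.8% |
| About 60% of 131 | 144 | 79 | 73.0% | 82.3% |
| All 131 usable | 144 | 131 | 84.7% | 91.0% |
| 10% loss in both cohorts | 129.6 | 64.8 | 65.8% | 76.5% |
| 20% loss in both cohorts | 115.2 | 57.6 | 60.8% | 72.2% |

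**Separating the two effects.** The fall from 80% to 70.4% is entirely the sidedness mismatch, since no control is missing and nobody is lost. The effect of the control count is the movement away from 70.4%: down 3.0 points at 65 controls, up 2.6 at 79. A 10% loss in both cohorts costs 4.6 points.

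**Can a larger new cohort offset too few controls?** With nc controls fixed, the new cohort needed for 80% is 1 / (1/m − 1/nc), where m = 60.46 two-sided or 47.62 one-sided.

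- Two-sided: 378 new patients at 72 controls and 865 at 65; no finite number at 60 or fewer.
- One-sided: 141 at 72 and 179 at 65; no finite number at 47 or fewer.

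**The case against.** The strongest reply is that the plan labels the 72 as historical controls, so 2:1 may simply describe the intended ratio of new to existing patients. The pool of 131 exceeds 72, and omitting the split from the protocol does not mean that nobody knows it. Allocation in the earlier studies was by place of residence, so an even split has no special standing; a Phoenix share above 55% would supply more than 72. On the broader wording in the introduction, all 131 might be used, which gives 84.7% two-sided. And 144 may be meant as the number analysed, with more enrolled.

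Much of this stands. A reader might infer that the 72 controls do not exist, that they were never counted, or that lost power cannot be restored. The documents support none of these. They are silent on the split and on week-8 completeness, and restoring 80% is impossible only at 60 or fewer controls two-sided (47 or fewer one-sided). Above those limits more new patients would achieve it, although the two-sided numbers soon become impractical. Nor does the word randomization in section 6 show that random allocation was intended; in a single-arm study it reads as leftover wording, and it has no effect on the calculation.

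The reply does not touch the first result. Even with all 72 controls and no loss, the stated inputs give 70.4%. It also does not supply the missing count or a loss allowance.

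Two cautions apply. The exact one-sided match is a match, not an explanation: an SD of about 5.6 would also give 72 controls two-sided (1.5 × (5.6 × 2.8016 / 2.27)² = 71.7), but the stated SD is 6.3. And 6.3 is a baseline SD, whereas the primary outcome is change from baseline, so every power figure here inherits the plan's own substitution.

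**Conclusion.** The point holds in two parts.

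The first is firm and rests only on section 3: 144 against 72 does not give 80% power at two-sided 0.05. It gives 70.4%, and the stated level at 2:1 needs about 273 patients. Equivalently, 144/72 has 80% two-sided power for about 2.55 s, not 2.27 s.

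The second is a gap in reporting. The controls form a closed set that includes conventional-physiotherapy patients, the number of eligible unilateral patients with both TUG values is not given, and no loss to week 8 is allowed for. Actual evaluable numbers may therefore fall on either side of 144/72. Over the assumed examples, two-sided power runs from 60.8% (20% loss in both cohorts) to 84.7% (all 131 usable and no loss). Taking the Phoenix groups as the comparator is an inference from the hypothesis, because the introduction also describes the comparison more broadly.

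**What to change.** In section 3:

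- Replace the 2:1 allocation rate and the fixed 72 with all unilateral-programme patients from the two feasibility studies who have baseline and week-8 TUG, and state that number.
- State an expected loss to week 8 and take 144 minus that loss as the evaluable new cohort.
- Restate two-sided power for 2.27 s, or the detectable difference at 80% power, for those numbers. At 144/72 these are 70.4% and about 2.55 s.

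In section 6, removing the word randomization is a clerical correction.

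The cost is one count from the existing database and revised wording in two sections, with no extra enrolment. The downside is that the stated power will probably be less favourable than 80%.

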c) Range of motion of the hip and knee

Hip and knee range of motion will be assessed based in three distinct positions: lying, sitting and standing. The system used in the study is a validated medical device for joint angle measurement. Therefore, knee range of motion will be measured automatically by the system.

In this study, the active range of motion will be measured through the following movements:

| Knee: | Hip: |
|------------------------|-----------------------------|
| Lying knee flexion | Lying hip flexion |
| Sitting knee flexion | Lying hip abduction |
| Standing knee flexion | Standing hip flexion |
| Sitting knee extension | Standing hip abduction |
| | Standing hip hyperextension |

To assess range of motion, the investigator will need to:

- 1) Create a patient profile in the Portal
- 2) Prescribe one set of each exercise, with 5 repetitions
- 3) Ask the patient to perform the session through the App, executing each repetition to the best of his ability
- 4) After the session, login to the Portal, go to the session's results and click on detailed results for each exercise. Record the flexion or extension angle of the best repetition for each exercise in the patient file.

10. Patient assessment

Patients will be assessed at baseline (pre-operatively) (A1), upon discharge (A2), at 4 weeks after rehabilitation program initiation (A3), and at the end of it (A4).

Assessments will be performed within a time window of 5-working-days, previous or ahead of the day the assessment was scheduled for.

Baseline assessment (A1)

Participant characterization will consist of:

- Demographics (gender, age at enrollment);
- Educational level (years at school);
- Diagnosis and affected side
- Date of surgery

- Height, weight, body Mass Index
- Comorbidities
 - Smoking
 - Diabetes
 - Cardiac disease
 - Respiratory disease
 - Hypertension
 - Stroke
 - Renal Disease
 - Bleeding disorders
 - Previous hip/knee replacement
 - American Society of Anesthesiologists physical status classification score of 3 or 4⁴²

b) HOOS/KOOS score

c) Timed Up and Go (TUG) test score

d) Hip and knee active range of motion

Assessment upon discharge (A2)

Patients will be reevaluated immediately upon hospital discharge, and the following parameters will be registered:

- Surgery date
- Operative time
- Type of prosthesis
- Adverse effects before discharge

Subsequent assessments (A3 e A4)

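### City residents can enter the bilateral cohort, but the earlier Phoenix arms (the implied unilateral control) held only patients from outside the city, and the plan neither records nor handles residence

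*Combined protocol and SAP*

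**What the plan says.** The introduction describes the two feasibility studies that supply the historical control. Treatment there was not randomised: "Geographical location was used as the allocation criterion". One half of the rule had "patients living within the city's administrative limits allocated to the conventional physiotherapy group". The other half had "patients living outside the city's administrative limits allocated to the experimental group". The experimental group used SWORD Phoenix at home.

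For the new single-arm study, the introduction says "The clinical outcomes will be compared to those of the above-mentioned feasibility studies", without naming an arm. The hypothesis that follows is that "the clinical outcomes of the bilateral exercise program will be superior to those of the unilateral exercise program". Section 3 sizes the comparison at 144 new patients against 72 historical controls and does not say which arm supplies the 72.

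Under section 6, "All patients admitted for total hip or knee replacement during the study period will" be screened. The only residence rule is criterion h in section 5, which excludes "Patients residing outside a 30km radius from the investigation center". No criterion turns on the city limits.

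The baseline assessment (A1) in section 10 begins with "Demographics (gender, age at enrollment", then lists education, diagnosis, body size and comorbidities. Residence is not listed. Section 15 defines intention-to-treat and per-protocol analyses of change from baseline to 8 weeks, and mentions no matching, restriction or covariate adjustment.

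**The concern.** Any historical control may differ from the new cohort in unknown ways. Here one difference is known in advance, because it comes from the allocation rule of the earlier studies and the eligibility rule of this one. A city resident could not have been in an earlier Phoenix arm but can be in the bilateral cohort.

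If patients inside and outside the city differ in TUG change for reasons unrelated to the exercise programme, that difference is counted as an effect of bilateral exercise. It could create an apparent benefit or hide a real one. The plan states a superiority hypothesis and a powered comparison, so describing the study as exploratory does not remove the problem.

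**Working it through.** **Eligibility by residence and programme**

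| Residence | Earlier Phoenix (unilateral) | Earlier conventional physiotherapy | New cohort (bilateral) |
|---|---|---|---|
| Inside city limits | none, by the allocation rule | yes | eligible, if within 30 km |
| Outside city limits | yes | none, by the allocation rule | eligible, if within 30 km |

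The only unilateral Phoenix cell lies outside the city. Pooling both earlier arms as control would give city residents a counterpart, but one treated with conventional physiotherapy. Residence and treatment would then be fully confounded within the control.

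**The plan's sample size.** Inputs from section 3: difference 2.27 s, SD 6.3 s, 80% power, two-sided 0.05, 2:1. Controls needed = 1.5 × [6.3 × (1.960 + 0.842) / 2.27]² = 90.7, so 91 + 182 = 273, not the stated 216. With one-sided 0.05 (1.645 in place of 1.960) the result is 72 + 144 = 216. This is a separate matter. It is relevant here because 144 against 72 starts from about 70% two-sided power, not 80%.

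**Possible bias.** Let f be the city share of the new cohort and D the difference in mean TUG change between city and non-city patients on the same programme. The new cohort's mean is shifted by f × D and the Phoenix control by nothing, so the bias is f × D. The documents give neither quantity. Assumptions: f from 20% to 60%, D from 0 to 2 s, either sign.

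- Smallest: D = 0 gives 0 s.
- Largest: 0.6 × 2 = 1.2 s, and 1.2 / 2.27 = 53% of the target difference.
- The standard error at 144 against 72 is 6.3 × √(1/144 + 1/72) = 0.91 s. With no true effect, a bias of 0 to 1.2 s gives a two-sided type I error of 5% to about 26%.

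**Cost of restricting to non-city patients.** The new patients left are 144 × (1 − f): 115, 86 or 58 for f = 20%, 40% or 60%. All 72 controls stay, because Phoenix controls are already non-city. Power is approximately Φ(2.27 / SE − 1.96), with SE = 6.3 × √(1/n + 1/72).

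| New patients (n) | √(1/n + 1/72) | Ratio to all 144 | Power for 2.27 s |
|---|---|---|---|
| 144 | 0.1443 | 1.00 | about 70% |
| 115 | 0.1503 | 1.04 | about 67% |
| 86 | 0.1597 | 1.11 | about 62% |
| 58 | 0.1764 | 1.22 | about 53% |

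These use the plan's SD, which is that of baseline TUG and not of the change, and its figure of 72 controls.

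**The case against.** The strongest reply is that no residence effect has been shown. Nothing in the documents links living inside the city to TUG change, and a difference of zero is possible. Several routes by which residence might act (age, years of schooling, comorbidity) are already in the section 10 baseline list and could be adjusted for without a residence field. Narrowing the main comparison to a subset would also weaken a test that is already short of power. All of this stands. It limits the size of the point and the strength of the remedy, but section 15 plans no adjustment even for the recorded variables, and nothing in the text removes the mismatch.

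Two premises are also open. The available text does not name the new study's centre, so city residents falling within 30 km assumes the same or a nearby site. The comparator arm is implied by the hypothesis but not stated.

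A reader might go further and infer that some earlier Phoenix patients lived beyond 30 km and would fail criterion h. The documents do not support that. The introduction only summarises the feasibility studies and does not give their eligibility criteria, so its silence on distance shows nothing either way. A reader might also infer that the comparison is biased in favour of the bilateral programme, or that the effect can be recovered only by making the restricted comparison primary. Neither follows, since the direction is unknown and the choice of primary comparison is a trade-off between bias and precision.

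**Conclusion.** The mismatch holds on the text, given the two assumptions about centre and comparator: otherwise eligible city residents enter the bilateral cohort with no counterpart in the unilateral control, and the plan neither records nor handles it. Its consequence is unquantified. The 0-1.2 s range rests wholly on the assumed shares and differences, includes zero, and has no known sign. That justifies a cheap safeguard fixed before analysis. It does not establish that the planned comparison is wrong or that its primary population must change.

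**What to change.** 1. In section 10, add to the baseline record whether the patient lives inside or outside the city limits used in the feasibility studies. Residence must already be known to apply criterion h.
2. In section 15, state that the superiority comparison uses the earlier Phoenix arms as control.
3. In section 15, pre-specify a sensitivity analysis restricted to patients living outside the city limits, or with a residence term in an additive model. With Phoenix-only controls and no other covariates, both take the treatment effect from non-city patients alone. Report it alongside the main comparison before claiming superiority over the unilateral programme.

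The cost is one baseline field and two sentences, with no extra patients or procedures. Historical city or non-city status is known from the arm, so no address check is needed. The downside is precision: under the assumed shares the sensitivity analysis has the larger standard error and lower power tabulated above, so a non-significant result there should be read through its estimate and interval and not taken as evidence of no effect.
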